4.0 Study Objective

4.1 Primary Objective

The primary objective of Study M16-244 is to assess the safety and tolerability of risankizumab in PsA subjects who have completed all doses of study drug and the Week 24 visit in Study 1311.5.

4.2 Secondary Objectives

Secondary objectives include the assessment of efficacy of risankizumab and the impact of risankizumab on the inhibition of structural progression in PsA subjects who completed all doses of study drug and the Week 24 visit in Study 1311.5.

5.0 Investigational Plan

5.1 Overall Study Design and Plan: Description

This is a 52-week multicenter, single-arm, OLE study to assess safety, tolerability and efficacy of risankizumab in PsA subjects who have completed all doses of study drug and the Week 24 visit of Study 1311.5 (Phase 2 randomized clinical trial in PsA subjects, sponsored by Boehringer Ingelheim).

Subjects who complete all doses of study drug and the Week 24 visit in Study 1311.5, meet all inclusion criteria (Section [5.2.1](#)) and none of the exclusion criteria (Section [5.2.2](#)) have the option to sign the informed consent form and enter the OLE study, receiving risankizumab 150 mg administered every 12 weeks with an additional dose of risankizumab made available at the Week 4 visit for those subjects that have not achieved a protocol defined response (defined as an improvement in tender and swollen joint count of $\geq 20\%$ compared with the baseline in Study 1311.5), provided the investigator believes this may be beneficial to the subject.

If the Study M16-244 Week 0 visit occurs on the same day or in the 4 days following the Study 1311.5 Week 24 visit only selected activities are required as some activities are common to both studies and are not required twice. See Study Activity Table in [Appendix C](#). If the OLE Week 0 visit occurs > 4 days and ≤ 8 weeks after the Study 1311.5 Week 24 visit, all procedures specified in [Appendix C](#) at Week 0 visit are required.

Subjects that enroll in the OLE study are no longer enrolled in Study 1311.5 and will not complete the Week 28 or Week 32 visits in Study 1311.5.

Subjects who are not enrolled in Study M16-244 within 8 weeks of the Study 1311.5 Week 24 visit are not eligible to participate in Study M16-244.

The study is anticipated to enroll up to 180 subjects. Study visits will occur at Week 0/Enrollment, Weeks 4, 12, 24, 36, 48 and 52. A \pm 4 day window is permitted around scheduled study visits after enrollment.

36-Week Treatment Period

[figure not shown]
Administration of study drug will occur at Week 0, 12, 24 and 36, with an additional dose of rizankizumab made available at the Week 4 visit for those subjects that have not achieved a protocol defined response (defined as an improvement in tender and swollen joint count of \geq 20% compared with the baseline in Study 1311.5), provided the investigator believes this may be beneficial to the subject. Subjects who have not attained a protocol defined response at 2 consecutive visits at Week 12 visit or thereafter, will be discontinued from the OLE study. Other criteria leading to discontinuation of individual subjects in this trial are described in Section [5.4.1](#).

A \pm 4-day window is permitted around scheduled study visits after enrollment. If any visit has to be rescheduled, subsequent visits should follow the original visit date schedule.

Follow-Up Period

Subjects will have follow-up visits at Week 48 and 52 and a Follow-up Phone call 20 weeks after the last dose of study drug. All Follow-up Visit procedures are noted in [Appendix C](#). Subjects who discontinue study drug treatment early will need to attend an early End of Treatment (EOT) visit ideally within 2 weeks after the decision and preferably prior to the administration of any new therapies. An End of Study (EOS) visit 16 weeks after the last dose of study drug and a Follow-up Phone Call 20 weeks after the last dose of study drug is required to determine the status of any ongoing AEs/SAEs or the occurrence of any new AEs/SAEs (see [Appendix C](#) and Section [5.4.1](#)).

A schematic of the study design is shown below in [Figure 2](#).

Figure 2. Study M16-244 Study Design

5.2 Selection of Study Population

5.2.1 Inclusion Criteria

1. Subjects who have completed all doses of study drug and Week 24 visit of Study 1311.5.
2. Women of childbearing potential must agree to use at least one of the following methods of contraception throughout the study including 20 weeks after the last study drug dose is given.
 - combined (estrogen and progestogen containing) hormonal birth control (oral, intravaginal, transdermal) associated with inhibition of ovulation initiated at least 1 month prior to study participation.
 - progestogen-only hormonal birth control (oral, injectable, implantable) associated with inhibition of ovulation initiated at least 1 month prior to study participation.
 - bilateral tubal occlusion/ligation
 - intrauterine device (IUD)
 - intrauterine hormone-releasing system (IUS).
 - Vasectomized sexual partner(s) (the vasectomized partner(s) should have received medical assessment of the surgical success and is the sole sexual partner of the trial participant).

- True abstinence: Refraining from heterosexual intercourse when this is in line with the preferred and usual lifestyle of the subject (periodic abstinence [e.g., calendar, ovulation, symptothermal, post-ovulation methods] and withdrawal are not acceptable).

Women of childbearing potential are defined as having experienced menarche and are:

- not postmenopausal (12 months with no menses without an alternative medical cause) and are
- not permanently sterilized (e.g., hysterectomy, bilateral oophorectomy or bilateral salpingectomy).

3. Women of childbearing potential must have a negative urine pregnancy test at Baseline (Week 0/V1).
4. Subjects must voluntarily sign and date an informed consent, approved by an Independent Ethics Committee (IEC)/Institutional Review Board (IRB), prior to the initiation of any study specific procedures.
5. Subject is judged to be in good health as determined by the Investigator.

See [Appendix D](#) for inclusion criterion specific to France.

Rationale for the Inclusion Criteria:

- 1, 5 To select the adequate subject population
- 2, 3 The impact of risankizumab on pregnancy and reproduction is unknown
- 4 In accordance with harmonized Good Clinical Practice (GCP)

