- Subject is significantly non-compliant with study procedures which would put the subject at risk for continued participation in the trial in consultation with the AbbVie study designated physician.

If, during the course of study drug administration, the subject prematurely discontinues study participation, the procedures outlined for the early EOT visit must be completed, ideally within 2 weeks of the decision and preferably prior to the initiation of another therapy. However, these procedures should not interfere with the initiation of any new treatments or therapeutic modalities that the Investigator feels are necessary to treat the subject's condition. For subjects that prematurely discontinue, study drug will not be given at the early EOT visit and subjects should attend their EOS Visit 16 weeks after last study drug dose and complete a Follow-up Phone Call 20 weeks after the last dose of study drug to determine the status of any ongoing AEs/SAEs or the occurrence of any new AEs/SAEs (see [Appendix C](#)).

Subjects who prematurely discontinue from study drug will not be required to collect x-rays at a designated time point, unless they received a dose within the 16 weeks prior to the scheduled time point.

All attempts must be made to determine the primary reason for premature discontinuation. The information will be recorded on the appropriate eCRF page.

For subjects that are considered lost to follow-up, reasonable attempts must be made to obtain information on the final status of the subject. At a minimum, two phone calls must be made and one certified letter must be sent and documented in the subject's source documentation.

Subjects who discontinue the study prematurely will not be replaced.

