6.1.6 Pregnancy

Pregnancy in a study subject must be reported to AbbVie within 1 working day of the site becoming aware of the pregnancy. Subjects who become pregnant during the study must be discontinued (Section 5.4.1).

Information regarding a pregnancy occurrence in a study subject and the outcome of the pregnancy will be collected.

Pregnancy in a study subject is not considered an adverse event. However, the medical outcome of an elective or spontaneous abortion, stillbirth or congenital anomaly is considered a serious adverse event and must be reported to AbbVie within 24 hours of the site becoming aware of the event.

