- j. Urine pregnancy testing will be done locally and prior to administration of study drug at all dosing visits and at each follow-up visit. Any subject with a positive urine pregnancy test must have a negative serum test performed at the central laboratory prior to enrollment or continuation in the study.
- k. Complete lab sample collection after PRO, clinical assessments and before study drug administration.
- l. In the event of a suspected hypersensitivity reaction or other systemic post-dose reaction, a PK/ADA and urine samples will be collected once within 24 hours of the reaction.
- m. For subjects that presented with inflammatory spondylitis at baseline to Study 1311.5 based on investigator judgment.
- n. Quantiferon[®] TB test or PPD (purified protein derivative) skin test will be performed according to local labelling for comparator products. If the result is positive, subjects may continue in the study if further work up (according to local practice/guidelines) establishes conclusively that the subject has no evidence of active tuberculosis. If presence of latent tuberculosis is established, then tuberculosis treatment may be deferred until completion of the trial according to clinical judgment of investigator and local country guidelines and it is also necessary to report it as an adverse event in the source documents and eCRFs. If the subject is diagnosed with active tuberculosis, the subject should not receive any further study drug and follow the premature treatment discontinuation procedure (Early EOT visit) in Section 5.4.1.
- o. Local tolerability at the administration site of the previous subcutaneous injection will be assessed by the investigator according to "swelling," "induration," "heat," "redness," "pain," or "other findings." Any abnormal findings at the injection site during the current visit will be reported as AEs.
- p. The additional dose is given in the event that the subject has not achieved a protocol defined response (defined as an improvement in tender and swollen joint count of $\geq 20\%$ compared with the baseline in Study 1311.5) and the investigator believes this may be beneficial to the subject.
- q. Subjects should be closely monitored for signs and symptoms of hypersensitivity reactions for approximately 2 hours following the first administration, and for approximately 1 hour following subsequent doses, of study drug. Hypersensitivity reactions should be treated according to medical standards.

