Appendix U. Follow-up Phone Call

Site Name/Number: _____ / _____

Subject Number: _____

Contact subjects that signed the protocol Amendment 1 ICF approximately 140 days (20 weeks) following last study drug administration.

Date of Call/Visit: _____

- Lost to Follow-up (check this box if subject was not willing to provide any follow-up information or you were unable to speak to the subject following at least two phone call attempts and one certified letter).
- No Events Reported

At the Follow-up Phone Call:

- Record any adverse events (AEs) and/or serious adverse events (SAEs) that occurred since the subject's last study visit. Document all AEs/SAEs in source records and EDC system. Report all SAEs to AbbVie within 24 hours of awareness of the event.
- Request update to the status of any AE that was ongoing at the last study visit.
- Request update to any concomitant medication(s) that was ongoing at the last study visit. Record any change in concomitant medication in source documents and EDC.

Name of person completing form (printed): _____

Risankizumab/ABBV-066
M16-244 Protocol Amendment 1
EudraCT 2016-003113-94

Signature of person completing form: _____

Date: _____

Please email this completed form to [REDACTED]

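### Contraception is required for 20 weeks after the last dose, but pregnancy is not actively ascertained in the last 4 of those weeks because the 20-week call form has no pregnancy item

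*Protocol*

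**What the plan says.** **Contraception period.** Protocol 5.2.1, criterion 2, requires contraception "throughout the study including 20 weeks after the last study drug dose is given". Section 5.2.4 repeats the 20 weeks. The rationale under 5.2.1 is that the effect of risankizumab on pregnancy and reproduction is not known. Section 1.1 records that Amendment 1 lengthened the period from 16 to 20 weeks and added a follow-up call at 20 weeks.

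**Testing and counselling.** Appendix C, footnote j: "Urine pregnancy testing will be done locally and prior to administration of study drug at all dosing visits and at each follow-up visit". Section 5.3.1.1 also ties the review of pregnancy avoidance to visits. Dosing is fixed in Section 5.1: "Administration of study drug will occur at Week 0, 12, 24 and 36". Section 5.4.1 places the "EOS Visit 16 weeks after last study drug dose" for subjects who stop early, and Section 5.1 gives the same interval.

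**The 20-week call.** Appendix U instructs the site: "Contact subjects that signed the protocol Amendment 1 ICF approximately 140 days (20 weeks) following last study drug administration". Its first item is "Record any adverse events (AEs) and/or serious adverse events (SAEs) that occurred since the subject's last study visit". The other two ask for the status of ongoing AEs and for changes in ongoing concomitant medication. Sections 5.1 and 5.4.1 describe the call's purpose in terms of AEs and SAEs only.

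**Status of pregnancy.** Section 6.1.6: "Pregnancy in a study subject is not considered an adverse event". The same section requires a pregnancy to be reported within 1 working day of the site learning of it, says that occurrence and outcome will be collected, and classes abortion, stillbirth and congenital anomaly as SAEs.

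**The concern.** Amendment 1 extended the obligation on women by four weeks and added a contact at the end of that period, but it did not give that contact the task of finding out whether a pregnancy had occurred. Because pregnancy is not an AE under Section 6.1.6, a site that follows the Appendix U form exactly will ask about AEs and medication and will not ask about pregnancy.

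The call is the last scheduled contact. A pregnancy not raised there may never reach the sponsor, and then neither the exposure nor the outcome is followed. Section 6.1.6 commits to collecting both, and where the reproductive risk is unknown each exposed pregnancy is informative.

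**Working it through.** This is calendar arithmetic plus a rough check of scale. No sample-size or error-rate figure is involved.

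**Inputs**
- Contraception period: 20 weeks after the last dose (5.2.1, 5.2.4).
- Last scheduled dose: Week 36, Day 253 ± 4 (5.1, Appendix C).
- EOS visit: Week 52, Day 365 ± 4 (Appendix C).
- Call: Week 56, Day 392 ± 4 (Appendix C); about 140 days after the last dose (Appendix U).
- Contraceptive failure rate: below 1% per year with consistent and correct use (5.2.4).
- Enrolment: up to 180 (5.1). The number of women of childbearing potential is not given; I assume 30 to 180.

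**1. Reproduce the plan's own figure.** 20 × 7 = 140 days, as Appendix U states. Week 36 + 16 = Week 52 and Week 36 + 20 = Week 56, as in Appendix C. On the table's days, 365 − 253 = 112 days (16 weeks) and 392 − 253 = 139 days, one day short of 140.

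**2. Gap between the last test and the end of the contraception period, for a subject who completes dosing.**
- Nominal: (253 + 140) − 365 = 28 days, which is 28/140 = 20% of the post-dose period.
- Shortest with ± 4-day windows: (249 + 140) − 369 = 20 days.
- Longest: (257 + 140) − 361 = 36 days.

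**3. Does anything scheduled in that gap detect a pregnancy?** Footnote j puts tests at dosing and follow-up visits, and there is no visit after EOS. None of the three Appendix U items asks about pregnancy. I place no weight on the missing Week 56 mark in the Pregnancy Test row of Appendix C. The AE and concomitant-therapy rows show no call mark in the available text either, although Appendix U collects both. The point rests on footnote j, Appendix U and Section 6.1.6.

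**4. Scale.** Expected pregnancies = n × 0.01 × gap/365.25.
- n = 30, 28 days: 30 × 0.01 × 28/365.25 = 0.02.
- n = 180, 28 days: 180 × 0.01 × 28/365.25 = 0.14.
- Over 20 to 36 days: 0.016 (n = 30, 20 days) to 0.18 (n = 180, 36 days).

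The upper end treats every subject as a woman of childbearing potential, which cannot be right in a trial of both sexes. On the other hand, the 1% ceiling presumes correct use.

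**5. After the fix.** With a pregnancy question at the call, the nominal stretch without active ascertainment falls from 28 days to 0, or to 1 day if the call is on Day 392 (393 − 392).

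**The case against.** The strongest reply is that passive capture remains. Section 6.1.6 has no end date for reporting a pregnancy the site learns of. Section 5.3.1.1 provides for a subject reporting that she is pregnant. Section 13.0 ends the study at the later of the last visit and the call, so a pregnancy mentioned at the call is still within the study. The medication item might bring out a stopped hormonal contraceptive. Losses and anomalies are SAEs, which the call does ask about.

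This stands to the extent that a reader should not infer that such pregnancies will be missed; they could be. The consent form is also not available here and may tell subjects to report a pregnancy. But these routes depend on the subject volunteering the information. The SAE route is thin, because a pregnancy that began after the EOS test is only a few weeks old at the call, too early for a stillbirth or a congenital anomaly to have appeared.

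Three other stronger readings lack support:
- **A longer gap.** One might add the days before the EOS test in which a very early pregnancy would not show. The documents give no figure for that, and the same limit would apply to asking at the call.
- **The same gap for every early stopper.** Sections 5.1 and 5.4.1 time EOS from the last dose, but the Appendix C column header times it as 16 weeks after EOT or early EOT. On the header's reading, a subject whose early EOT visit falls 4 or more weeks after the last dose is tested at or after 20 weeks and has no gap.
- **A wrong figure in the safety report.** The SAP plans no pregnancy summary. Pregnancy appears there only as a screening test in Section 7.1.

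**Conclusion.** The point holds as a gap in active ascertainment. For subjects who complete dosing, the last 28 days of the contraception period (20 to 36 with windows) contain neither a test nor a question, and a pregnancy then is recorded only if it is volunteered or ends in a reportable SAE. The defect lies in Appendix U, read with Appendix C footnote j and Section 6.1.6. Inclusion criterion 2 itself is sound.

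The expected number is well below one: about 0.02 to 0.14 over 28 days, on the 1% per year ceiling and an assumed 30 to 180 women of childbearing potential. No planned estimate or conclusion changes. The matter is completeness of safety data and follow-up of exposed pregnancies. It is worth correcting because the remedy costs very little and completes what Amendment 1 set out to do.

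**What to change.** 1. Add one item to Appendix U, and to the call column of Appendix C: ask women of childbearing potential whether a pregnancy has occurred or is suspected since the last visit, and report any under Section 6.1.6.
2. Name pregnancy in the purpose of the call in Sections 5.1 and 5.4.1.
3. Reconcile the timing of the EOS visit for early stoppers between the Appendix C header and Sections 5.1 and 5.4.1.
4. Reconcile the day of the Week 56 call: Day 392 ± 4 in the main Appendix C table, Day 365 ± 4 in the Japan table of Appendix D.

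The cost is one question in a call already made, the form and protocol wording, and possibly an extra pregnancy report to follow up. The question narrows the gap but does not close it: a very recent conception may be unknown to the subject at the call, and Appendix U limits the call to subjects who signed the Amendment 1 consent form.

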5.2.2 Exclusion Criteria

A subject will not be eligible for study participation if he/she meets any of the following criteria:

1. Female subject who is pregnant, breastfeeding or is considering becoming pregnant during study participation, including 20 weeks after the last dose of study drug is given.
2. Premature discontinuation of study drug in Study 1311.5 for any reason.
3. Use of a biologic treatment other than risankizumab since first dose of study drug in Study 1311.5.
4. Time elapsed is > 8 weeks since the Week 24 visit in Study 1311.5.
5. Active systemic infections during the last 2 weeks (exception: common cold) prior to randomization, as assessed by the investigator.
6. Anticipated requirement during the study or receipt of any live or attenuated vaccine since first dose administered in Study 1311.5.
7. Participation in another investigational study since first dose of study drug in Study 1311.5.
8. Current diagnosis of a major chronic inflammatory or connective tissue disease other than PsA (e.g., rheumatoid arthritis, systemic lupus erythematosus, ankylosing spondylitis, Lyme disease, gout) and fibromyalgia as assessed by the Investigator.
9. Use of any restricted medication as specified in this protocol or any drug considered likely to interfere with the safe conduct of the study, as assessed by the investigator, since first dose of study drug in Study 1311.5.
10. History of allergy/hypersensitivity to a systemically administered biologic agent or its excipients.
11. Chronic or relevant acute infections including HIV (human immunodeficiency virus), viral hepatitis and (or) active tuberculosis.
12. Any documented active or suspected malignancy or history of malignancy since first dose of study drug in Study 1311.5, except appropriately treated basal or squamous cell carcinoma of the skin or in situ carcinoma of uterine cervix.

13. Major surgery (including weight loss surgery), performed since first dose of study drug in Study 1311.5 or planned while study is ongoing as assessed by the investigator.
14. Evidence of a current or previous disease, medical condition (including chronic alcohol or drug abuse) other than PsA and PsO, surgical procedure (i.e., organ transplant), medical examination finding (including vital signs and electrocardiogram (ECG)), or laboratory value in Study 1311.5 outside the reference range that in the opinion of the investigator is clinically significant and would make the study participant unreliable to adhere to this protocol or to complete this trial, compromise the safety of the subject, compromise the quality of the data or for any reason cause the Principal Investigator (PI) to consider the subject an unsuitable candidate.

See [Appendix D](#) for inclusion criterion specific to France.

Rationale for Exclusion Criteria:

1	The impact of risankizumab on pregnancy and reproduction is unknown
2, 4, 8, 14	To select the adequate subject population
3, 5, 6, 7, 9 – 13	To ensure the safety of the subjects throughout the study

